The IT-solution functions with 'buttons' on a touch-screen. Each 'button' corresponds to one item. Thus the solution makes it easy to attain an overview of the items [41]. The solution has been approved by Center for IT, Medico and Telephone (CIMT) of the Capital Region, who requires that the actual programming is done by a private company (I-r software a/s). A four step validation process will follow the EORTC-guidelines for cross-cultural adaptation of QoL questionnaires [47] and include *linguistic and cultural validation*, but not psychometric, as the PCI is not a QoL questionnaire: (1) forward and (2) backward translation, (3) pilot testing a paper version by HNC patients (n=10) and patients from patient networks (Dansk Landsforening for Hals- og Mundhuleopererede and Netværk for hals og mundhulekræft). The testing will include interviews based on a brief structured questionnaire on the understand ability of the PCI [47]. (4) Finally, to ensure IT-solution suitability in clinical practice, it will be pilot tested by HNC patients (n=10), who will be interviewed on the basis of a brief questionnaire on the applicability and usefulness of the touch-screen solution. An in-depth validation protocol is attached (Appendix II). Two native Danish and English speaking persons will be asked to carry out the forward and backward translation. Patient recruitment for step 4 (n=10) and 5 (n=10) of the validation process will be identical. The inclusion and exclusion criteria are the same as in study two. The PCI and IT-solution will be tested and re-tested on new patients until problems with comprehensiveness is resolved. A final translation report will be sent to consultants at Aintree Hospital, Liverpool for approval.

Design and methods (Figure 1 attached)

The study is designed as a two arm randomized controlled study with a control group (CG) and intervention group (IG). Patients will be randomized via Research Electronic Data Capture (REDCap), an electronically based system for keeping research data, containing a randomisation module. Patients will be randomly assigned 1:1 to either CG or IG, stratified according to newly diagnosed and recurrences. The assignments will not be blinded to either investigator or patients.

Population and recruitment

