Total study population (n=128). CG (n=64) and IG (n=64) will be recruited consecutively during hospital admission post-surgery from April 2018 - March 2019. The inclusion and exclusion criteria will be the same as in study two.

Statistics

The sample size of this study (n=128) is based on a power calculation with an SD of 20; effect size 10 and power of 0,8. SD is based on similar studies on Head and Neck patients [48] and effect size on recommendations from EORTC [49], further the sample size is based on previous research in the Department of ORL H&N, Copenhagen University Hospital. To account for an expected dropout rate and non-recruitment rate of approximately 20% [50][51], the number of patients included in the study will be 160. Furthermore, based on the ratio between newly diagnosed patients and recurrences, we will stratify each study arm as follows; newly diagnosed (n=43) and recurrences (n=21).

Procedures

CG will receive standard care according to the Danish Health and Medicine Board's follow-up programme for HNC patients [52], which requires all patients have their physical, emotional, social and existential needs assessed by interview with a HCP, at three time-points post-treatment. At present this is done at the Dept. of ORL, H&N during the admission period post-surgery, two weeks and two months post-surgery, by a staff nurse who is a member of the rehabilitation team who perform nurse consultations. These consultations take place after the appointment with the surgeon. The nurse refers the patient to physical rehabilitation if needed.

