Quantitative outcomes: The primary outcome will measure the effect of the intervention by PRO quality of life and symptom questionnaire EORTC QLQ-H&N35. H&N35 is a 35-item questionnaire to be used with a core questionnaire[53]. The H&N module particularly measures oral pain, nutritional and voice problems. Patients will be asked to complete the EORTC QLQ-H&N35 at four time-points, 1) baseline (before randomisation) 2) between discharge and first follow-up in OPD 3) 7 days after first and 4) second post-surgical appointments – by telephone. Presence and severity of symptoms will be evaluated by MDASI-HN (MD Anderson Symptom Inventory) which is a multi-symptom patient-reported outcome measure for clinical and research use ([54]). MDASI-HN is a 28-item questionnaire which measures symptoms of HNC patients. Finally the patients physical activity level will be measured according to the Saltin-Grimby Physical Activity Level Scale, which

is a four-item questionnaire measuring the patients activity level [55]. MDASI-HN and Saltins will be used at four time-points – baseline (before randomization); before discharge; at first and second post-surgical appointment. Demographic and medical data (age, sex, diagnosis) will be registered at baseline and the types and number of multi-disciplinary referrals will be registered at each follow-up. The outcomes and items patients choose on the PCI will be registered. Finally the acceptance and adherence to the study will be assessed by registering the number of patients recruited and participating in the study and the attrition rate.

Qualitative outcomes: Qualitative interviews and focus group interviews will be carried out at the second post-surgical appointment to explore patient and HCP perspectives regarding the use of PCI. The interviews will be based on semi-structured interview guides. For the qualitative individual interviews, patients from IG (n= 15) will be recruited at the OPD, at the two-week appointment, from August to September 2018 and carried out October to November 2018. For the focus group interview, doctors and nurses (n=6-8) will be recruited at the Department from January - February 2019 and carried out March 2019.

Data and analysis

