The baseline demographic, medical data and number and types of referrals to multi-disciplinary team will be compared between the two trial arms using the chi-square test for categorical variables, the Student's t-test for normally distributed continuous variables, and the Mann-Whitney test for non-parametric variables. Descriptive data will be presented as means with standard deviations, medians with inter-quartile ranges or frequencies with percentage depending on the distribution of the variable. For the intervention group; feasibility, acceptance, adherence, attrition (and reasons) and safety will be calculated in mean and percentage. Data from the PRO questionnaires will be keyed in a database, compared across groups using SAS program to evaluate for statistical difference and effect size, by two-sample t-test. Analysis of covariance (ANCOVA) will be applied for comparisons of groups adjusted for, e.g. smoking and alcohol consumption status or sex.

Qualitative: The focus group interview and the individual interviews will be recorded digitally, transcribed verbatim and coded in the software program NVivo. Thematic analysis will follow a model where the transcriptions will be read and re-read, coded according to emerging themes, a clustering of themes and finally reaching a number of themes, which describes the patient's or HCP's experiences with the PCI in the new model of care [45]. Researcher triangulation will be applied.

A detailed project description for this part of the study will be developed.

Ethical considerations

Patients will receive oral and written information that participation is voluntary and that they may withdraw at any time without affecting treatment and care. Written informed consent will be obtained from patients participating at time of recruitment. The Regional Ethics Committee of the Capitol Region of Denmark has been approached regarding approval of the study. They have assessed this and deemed an approval unnecessary (Jr. no: 16036032)

The study has been approved by the Danish Data Protection Agency (RH-2017-264 ,I-Suite no: 05781) and will be sought registered at ClinicalTrials.com. The study will be carried out in accordance to the Helsinki Declaration and published according to Vancouver guidelines.

Clinical Perspectives

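### The PRO analysis names smoking, alcohol and sex as example covariates but not the baseline H&N35 score or the randomisation stratum, so it leaves available precision unused

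*Protocol*

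**What the plan says.** All places are in the protocol, Study three.

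- **Data and analysis.** PRO questionnaire data are "compared across groups using SAS program to evaluate for statistical difference and effect size, by two-sample t-test". The next sentence reads: "Analysis of covariance (ANCOVA) will be applied for comparisons of groups adjusted for, e.g. smoking and alcohol consumption status or sex". Neither method is ranked as primary.
- **Outcome measures.** The H&N35 is the primary outcome, and a pre-randomisation measurement is planned: "Patients will be asked to complete the EORTC QLQ-H&N35 at four time-points, 1) baseline (before randomisation"). Three later assessments follow. The baseline demographic and medical data are given as age, sex and diagnosis.
- **Design and methods.** "Patients will be randomly assigned 1:1 to either CG or IG, stratified according to newly diagnosed and recurrences".
- **Population and recruitment.** The two groups "will be recruited consecutively during hospital admission post-surgery".
- **Statistics.** The sample size of 128 rests on a "power calculation with an SD of 20; effect size 10 and power of 0,8". After an allowance of about 20% for dropout and non-recruitment, "the number of patients included in the study will be 160". The stratum sizes are also given: "we will stratify each study arm as follows; newly diagnosed (n=43) and recurrences (n=21").

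**The concern.** In a randomised trial with a continuous outcome, the most useful covariate is usually the baseline value of the same scale. The natural second one is any factor used to stratify the randomisation. Both are available here and neither is mentioned. Of the three examples that are mentioned, two (smoking and alcohol) do not appear among the listed baseline data. The word introducing the examples leaves the list open, so baseline and stratum are not ruled out, but nothing points to them either.

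What is at stake is precision. With 64 analysed per arm the t-test only just reaches 80% power. A covariate correlated with the outcome would narrow the confidence interval and give some protection if fewer patients are evaluable. There is also a smaller question of matching analysis to design: if the arms are balanced within strata, a test that ignores the stratum is conservative.

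**Working it through.** **Inputs.** From the protocol: SD 20, difference 10, power 0.80, 64 per arm, strata of 43 and 21 per arm, 160 included. Assumed: two-sided 5% level (not stated), SD 20 as the SD of a score at one time, and baseline–follow-up correlation r from 0.1 to 0.6.

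**1. The plan's own figure.** Two-sample t-test, noncentral t, with standardised difference 10/20 = 0.5. The required size is 63.8, so 64 per arm and 128 in total. Power at 64 per arm is 0.801. With 20% loss, 128/0.8 = 160. Both figures reproduce, and they take no credit for baseline. The standard error is 20 × √(2/64) = 3.54, and the 95% CI half-width is 7.0 points.

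**2. Adding the baseline score.** The residual SD is 20 × √(1 − r²), with 128 − 3 = 125 degrees of freedom. At r = 0.5, for example, the residual SD is 17.32 and the standard error 3.06.

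| r | Power, 64 per arm | CI half-width | n per arm for 80% power |
|---|---|---|---|
| t-test | 0.801 | 7.0 | 64 |
| 0.1 | 0.805 | 7.0 | 64 |
| 0.2 | 0.817 | 6.9 | 62 |
| 0.3 | 0.837 | 6.7 | 59 |
| 0.4 | 0.865 | 6.4 | 54 |
| 0.5 | 0.900 | 6.1 | 49 |
| 0.6 | 0.939 | 5.6 | 42 |

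Spending one more degree of freedom on the stratum leaves these powers essentially unchanged.

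**3. If evaluable numbers fall short.** At 60 or 56 per arm the t-test has power 0.775 or 0.746. ANCOVA at r = 0.4 has 0.842 or 0.816.

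**4. Adding the stratum.** Let D be an assumed difference in mean score between the strata. With p = 21/64, the stratum accounts for p(1 − p)D² of the total variance of 400. That is 5.5, 22.0 and 88.2 for D = 5, 10 and 20, or 1.4%, 5.5% and 22.0%.

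| Allocation | Result | D = 5 | D = 10 | D = 20 |
|---|---|---|---|---|
| Exact 43/21 in both arms | Type I error, unadjusted | 0.049 | 0.044 | 0.026 |
| | Power, unadjusted / adjusted | 0.803 / 0.807 | 0.808 / 0.823 | 0.830 / 0.889 |
| Balanced arms of 80, 20% random dropout | Type I error, unadjusted | 0.049 | 0.045 | 0.031 |
| | Power, unadjusted / adjusted | 0.802 / 0.805 | 0.805 / 0.821 | 0.822 / 0.887 |
| No blocking within strata | Type I error, unadjusted | 0.050 | 0.050 | 0.050 |
| | Power, unadjusted / adjusted | 0.799 / 0.801 | 0.798 / 0.817 | 0.797 / 0.884 |

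These are simulated, with 2,000,000 trials per case. An analytic check of the exact-balance row gives type I errors of 0.0484, 0.0438 and 0.0265. The stratum-adjusted test keeps 0.050 in all nine cases. The protocol does not describe blocking, so which row applies is not known. D = 20 is a full SD and serves as an upper bound.

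**The case against.** **Covariate lists belong in the SAP.** Only the protocol is at hand, it already plans an ANCOVA, and its list is open. It is true that nothing excludes baseline or stratum, and an SAP could add them. But the protocol itself names the test and gives covariate examples, so the point concerns what it states and not what it leaves out. An open list also commits the sponsor to no particular model.

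**The gain may be negligible.** This stands as a limit. Recruitment is after surgery, so the baseline is probably an early postoperative score, and a weak correlation with later scores is plausible. However, the change costs essentially nothing even then: at r = 0.1 power is still 0.805.

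**There may be more margin than 64 per arm suggests.** The 20% covers dropout and non-recruitment together, and the 160 are patients included. If only 10% drop out, 72 per arm are analysed and the t-test has power 0.846; with none lost, 80 per arm gives 0.882. That is fair. The split is not documented, and 64 per arm is the number the sample size calculation relies on.

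**SD 20 might be the SD of change scores.** The single-time SD would then be 20/√(2(1 − r)). The t-test on follow-up scores would already have power 0.96, 0.94 and 0.91 at r = 0.1, 0.2 and 0.3, and ANCOVA would add only 0.001 to 0.023. At r = 0.5 the two readings coincide, because 2(1 − 0.5) = 1, and the gain is again 0.80 to 0.90. The protocol does not say which SD is meant, and it does not mention change scores as the quantity analysed.

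**The outcome itself is not yet defined.** This is correct and comes first. Without a named scale and time point the ANCOVA cannot be written down.

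**Conclusion.** The point holds, as an optional improvement. The planned t-test is valid, and 128 and 160 are right for their inputs. What the plan leaves unused is the precision available from two covariates that the trial will already have.

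On the assumptions above, baseline adjustment raises power at 64 per arm from 0.80 to between 0.81 (r = 0.1) and 0.94 (r = 0.6), and shortens the CI half-width from 7.0 points to as little as 5.6. The size within that range is unknown because r is not documented. Stratum adjustment is negligible for a 5-point gap between strata and small for 10. Its main merit is that it keeps the type I error at 5% in every allocation case examined, whereas the unadjusted test is conservative when the arms are balanced within strata. Confidence is medium, chiefly because r, the meaning of SD 20 and the blocking scheme are not given.

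**What to change.** State in Study three, Data and analysis, that the primary H&N35 comparison is an ANCOVA of the follow-up score on arm, baseline score of the same scale, and newly diagnosed/recurrence stratum. Keep the two-sample t-test as a supportive analysis, and replace the open list of examples with a closed one.

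Name the H&N35 scale and the post-baseline time point first; three such assessments are planned and none is singled out.

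A minor drafting point: either add smoking and alcohol to the baseline data or drop them as covariates.

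The cost is a few sentences. The model needs no new data, since the baseline questionnaire is already planned and the stratum must be known in order to randomise. Keeping smoking and alcohol may add two baseline items. The sample size need not change.

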Publications: Four publications are planned: 1) Literature review: 'Early and late physical and psychosocial effects of primary surgery in patients with oral and oropharyngeal cancers: a systematic review' (published) 2) Qualitative study: An exploration of nurse-patient communication and interactions during rehabilitation consultations with Head and Neck cancer patients 3) Randomised controlled study: 'Needs assessment and decision-making tool integrated in clinical practice to enhance patient involvement in Head and Neck Cancer Rehabilitation' and 4. Qualitative findings: Feasibility and patient experiences of new needs assessment and decision-making tool integrated in clinical practice to enhance patient involvement in Head and Neck Cancer Rehabilitation. The articles will be published according to Vancouver guidelines in peer reviewed scientific journals as Head & Neck; Oral Oncology; Support Care Cancer; Cancer Nursing; European Journal of Cancer Care.

Conferences: The results will be presented at international conferences: Society of Otolaryngology, Head-Neck nurses (SOHN) annual congress; International Head and Neck Cancer Quality of Life Conference; Annual meeting on supportive care in cancer (MAASC), and national conferences: Nationalt Symposium for Fagligt Selskab for ØNH-kirurgiske sygeplejersker and Lanskursus for Fagligt Selskab for Kræftsygeplejersker.

References:

- [1] A. Jemal, F. Bray, M. M. Center, J. Ferlay, E. Ward, and D. Forman, "Global cancer statistics.," *CA. Cancer J. Clin.*, vol. 61, no. 2, pp. 69–90, Jan. .
- [2] Nordcan, "Nordcan - oral cavity & pharynx- Nordic Countries." [Online]. Available: <http://www-dep.iarc.fr/NORDCAN/english/StatsFact.asp?cancer=540&country=0>.
- [3] Nordcan, "Nordcan Nasopharynx Nordic Countries." [Online]. Available: <http://www-dep.iarc.fr/NORDCAN/english/StatsFact.asp?cancer=540&country=0>.
- [4] Nordcan, "Nordcan oropharynx Nordic Countries." .
- [5] Nordcan, "Nordcan oropharynx Denmark." [Online]. Available: <http://www-dep.iarc.fr/NORDCAN/english/StatsFact.asp?cancer=540&country=0>.
- [6] Nordcan, "Nordcan nasopharynx Denmark." [Online]. Available: <http://www-dep.iarc.fr/NORDCAN/english/StatsFact.asp?cancer=50&country=208>.
- [7] Nordcan, "Nordcan oral cavity and pharynx." [Online]. Available: <http://www-dep.iarc.fr/NORDCAN/english/StatsFact.asp?cancer=540&country=208>.

Appendix I

An exploration of nurse-patient interactions during nurse consultations with Head and Neck cancer patients - a qualitative study

1. Background:

Nurse-patient interaction is at the core of nursing care and may be planned with a therapeutic purpose or may occur spontaneously (in practice) (Evans 2016) involving physical, psychological, social and professional aspects as well as informative/instructional actions (Evans 2016). The interaction is often based on verbal as well as non-verbal communication, as many nursing interactions and procedures can be performed without verbal interaction (Evans 2016). Studies have shown that nurses tend to direct the goals of nurse-led consultations, but allow for patient participation (Tobiano et al. 2016)(Mayor and Bietti 2017)(Brataas, Thorsnes, and Hargie 2010). Communication is an important and integral part of much nurse-patient interaction (Evans 2016). There is a growing number of studies investigating communication between nurses and patients and the degree of patient involvement in head and neck cancer (HNC). These show that nurses generally are skilful at informing about and responding to patient's questions related to medical issues (de Leeuw et al. 2014), but find it more difficult to respond to emotional cues (de Leeuw et al. 2014)(Sheldon, Hilaire, and Berry 2011). It has been found that nurses may acknowledge the cues, but choose to distance themselves from these in communication with the oncological or HNC patient (de Leeuw et al. 2014)(Sheldon et al. 2011). Sheldon etc. al. found it to be important to be able to identify psychosocial needs in order to care for these needs or refer patients to professional support (Sheldon et al. 2011). However, studies have also shown that HNC patients prioritize medical information above emotional support (Jabbour et al. 2017)(Salander et al. 2016). Furthermore the preferred modality of information differs depending on the patient's educational level, and it has been shown that those of higher education have a preference for obtaining information from the Internet. However, all HNC patients prefer one-on-one communication/information from a healthcare professional(Jabbour et al. 2017)(Papadakos et al. 2017).

Finally studies have shown that patients coming from a background of short education, as some HNC patients do (Papadakos et al. 2017)(Olsen et al. 2015), are hesitant to express their own needs and need to be encouraged to do so (Protheroe et al. 2013). Nurse consultations take place in many settings in hospitals, however it is unclear what takes place in the interaction between the patient and nurse, during these consultations. Firstly it is not clear to which degree the patients find themselves involved in these consultations and secondly whether all patients, regardless of educational background, understand the information delivered during these consultations.

2. Aim

To explore nurse-patient interaction, patient involvement and communication practices during rehabilitation consultations in post-surgical patients with Head and Neck cancer (HNC).

3. Methods

An exploratory and descriptive qualitative study informed by ethnographic fieldwork. The study will include nonparticipant observations during nurse consultations (n=15), individual patient interviews (n=15) and focus group interviews with nurses performing nurse consultations (n=4), employing Interpretive Description (Thorne 2016)

Participants and setting:

Study participants will be recruited from Dept. ORL, H&N. Included are patients, who have been diagnosed and treated surgically for head and neck cancer, at stage T3 or T4, and able to speak and understand Danish. Excluded are patients treated surgically for thyroid or parotic cancers, patients referred to adjuvant radio – or chemotherapy and patients with unstable psychiatric illness.

Using purposive sampling, patients will be recruited in the post-treatment phase after surgery for Head and Neck Cancer in the bed ward before discharge, for interviews at three time points:

1. before discharge in the bed ward
2. 7 – 10 days post-operatively in the OPD
3. 2 months post-operatively in the OPD

Observations (n=5) and patient interviews (n=5) will be performed at each time point.

Procedure

Observations will be carried out by main investigator (AM), individual interviews by AM and research assistant (RM) and focus group interview by AM and research assistant (BN). Individual and focus group interviews will be based on separate semi-structured interview-guides. Interviews will be recorded digitally.

Observations will be recorded by AM as short handwritten field notes during observations and following this expanded as field notes in a text-file. AM will situate herself in the field as a researcher and be conscious about her own previous role as a clinical nurse specialist. In order to perform an inductive analytic process, AM will also make field notes on her own experiences as a researcher in the field (Thorne 2016)

Context - nurse rehabilitation consultations

In the Department of Otolaryngology, Head and Neck Surgery and Audiology, Rigshospitalet (Dept. ORL, H&N), formal nurse rehabilitation consultation takes place at three different time points post-surgically in Head and Neck cancer patients: 1. before discharge; 2. seven – ten days and 3. Two months postoperatively in the OPD. The purpose of the consultations are to evaluate the patient's need for rehabilitation after surgical treatment for HNC in the areas of physical, emotional, social and existential needs and refer patients to multi-disciplinary follow-up if needed.

Analysis

Data will be analysed using Interpretive Description (ID) (Thorne, Kirkham, and O'Flynn-Magee 2004) (Thorne 2016) which is an inductive analytic approach designed to create ways of understanding clinical phenomena that yield application implications. When applying ID a concurrent data collection and analysis will take place, inspired by ethnographic analysis.

The focus group interview and the individual interviews will be recorded digitally, transcribed verbatim, read and re-read in depth to get a preliminary understanding of the text, before coding in the software program NVivo (Bazeley and Jackson 2013). In order to conduct a constant comparative analysis using ID, the further sorting of interview – and observational data will apply systematic text condensation, using four steps: Total impression – from chaos to themes; Identifying and sorting meaning units - from themes to codes; Condensation – from code to meaning; Synthesizing – from condensation to descriptions and concepts (Malterud 2012).

Researcher triangulation will be applied.

4. Ethical issues

Based on the ethical guidelines provided by the Northern Nurses' Federation on nursing research in the Nordic countries (Federation 2003), the following ethical aspects of the project will be taken into consideration. The principles of autonomy; beneficence; non-maleficence and justice: this means that voluntary participation in the study will be ensured and any form of coercion avoided. Voluntariness will be based on oral and written information about the project. The information will be provided in such a manner that patients and nurses understand the purpose of the study and the consequences of their own participation, in this. Further is the self-determination of participants protected by ensuring that withdrawal from the project can take place without negative consequences.

The information/data patients and nurses provide through observations and interviews will be treated in (such a manner) that their integrity will be respected and anonymity provided and finally it is ensured that the research will not be harmful to the participants in any way.

Patients will be informed about observational studies through posters in Dept. ORL, H&N and individual patients will be asked to give oral consent to being observed prior to the observation. Nurses performing rehabilitation consultation will be informed through individual information and doctors and nurses through informational meetings and emails.

Patients who participate in individual interviews will receive oral and written information that participation is voluntary and they may withdraw at any time without affecting treatment and care. Written informed consent will be obtained prior to the interview. Nurses participating in focus group interview will receive oral and written information. Written informed consent will be obtained prior to the interview.

The study has been registered by The Regional Ethics Committee of the Capitol Region of Denmark (Jr. no: 16036032), the Danish Data Protection Agency (Jr. no: RH-2017-264, with I-Suite no: 05781) and will be registered with clinical trials.gov

The study will be carried out in accordance to the Helsinki Declaration.

5. Dissemination and outputs

Publication:

The study will be published according to Vancouver guidelines in peer reviewed scientific journals as Support Care Cancer; Cancer Nursing; European Journal of Cancer Care.

